Appendix A: Study Flow Chart

	Study Drug Treatment			Follow-up			Extended Follow-up
	Screening Baseline 1-2 days post injury (+/- 4 days)	12-14 days post injury	Surgery ⁵			6 Months Follow-up/Early Termination Visit	Sub-Study
Study Time points	Time point 1	Time point 2		1-2 Weeks post surgery	4-6 weeks post surgery		24 Months (+/- 3) post surgery
Procedures	Visit 1	Visit 2	Visit 3	Visit 4	Visit 5	Visit 6	Visit 7
Informed Consent	X						X
Partial Medical History	X						X
Medication History	X	X	X	X	X	X	X
Smoking Status	X						
BMI Measurement	X						

Demographics	X						
X-Ray ¹	X						
MRI ^{2,6}	X						X
Range of Motion	X						X
Knee Aspiration	X	X	X ^{3&5}	X ^{3&5}			
Randomization	X						
Study Medication	X	X					
Laboratory Tests							
Urine	X	X	X				
Blood	X	X	X				
Questionnaires And Scales							
Likert Pain Scale ⁴	X	X	X	X	X	X	X
CSQ	X	X	X	X	X	X	X
KOOS	X	X	X	X	X	X	X
IKDC	X	X	X	X	X	X	X
SF 36	X	X	X	X	X	X	X
Catastrophizing Scale	X	X	X	X	X	X	X
MARX Activity Scale							X

- 1 = All subjects must have standardized flexion weight bearing x-rays. *Documentation of closed growth plates at screening will be noted on the routine SOC x-rays.*
- 2 = All subjects enrolled will have an MRI performed as a routine diagnostic tool regardless if surgery is to be scheduled or not. However, randomization can be performed prior to MRI as the MRI examination is not necessary or required to diagnose the ACL tear.
- 3 = Knee aspiration will only be performed if the subject has post-op fluid on the knee. Should a subject be enrolled into the study and choose not to undergo ACL reconstruction, aspiration at time of surgery will be omitted.
- 4 = All subjects enrolled into the study must have been diagnosed with an ACL tear.
- 5 = Should a subject be enrolled into the study and choose not to undergo ACL reconstruction, subject will receive treatment according to this protocol.
- 6 = Subjects enrolled into the extended follow-up sub-study will undergo a research specific MRI, that is not considered standard of care.

References:

Patients who suffer anterior cruciate ligament (ACL) tears commonly undergo surgical reconstruction. While surgical techniques have consistently been improved to be more anatomic, the long term consequences such as posttraumatic osteoarthritis and subsequent pain have not been significantly reduced. In fact, over 50% of all young patients with ACL tears will develop radiographic OA osteoarthritis (OA) within 10 years after injury.

The long-term consequences of post-traumatic OA include arthrofibrosis, pain, limited motion, and recurrent instability. Because ACL injuries occur most often in younger individuals (average age 14-29 years), pain and other debilitating symptoms occur most often during patients' most productive years. Current surgical and non-surgical treatment options for ACL injury, while relatively successful in restoring function and stability in the short term, do little or nothing to reduce the risk of post-traumatic OA later in life.

ACL rupture, with or without accompanying damage to nearby cartilage and bone, initiates a persistent cascade of inflammation and catabolic enzyme activity leading to OA of the articular cartilage in the knee joint. We propose to disrupt the inflammation-driven cascade with Triamcinolone (Kenalog®). We hypothesize that Triamcinolone administered intra-articularly during the early phase of acute ACL injury will provide symptomatic pain relief and decrease synovial fluid inflammatory and cartilage degradation markers. We will test our hypothesis in a multicenter, randomized, placebo controlled, double blinded, clinical trial.

Unlike primary OA, which typically strikes older individuals and develops silently over the course of many years, post-traumatic OA is thought to begin at the moment of ACL injury in many individuals. Capitalizing on the expertise and experience of our collaborative team of investigators, we have chosen to seize this window of opportunity and provide the field with valuable new data regarding the importance and amenability of pain control in acute ACL injury. Our proposed study will also generate robust preliminary data that will be used to inform a larger randomized clinical trial with our collaborators at the Multicenter Orthopaedic Outcomes Network (MOON; PI [name], Vanderbilt University, TN) cohort of ACL injury.

Study Drug - Triamcinolone, is manufactured by Bristol-Meyer-Squibb, New York NY (Kenalog), is available as 1ml (40mg) vials and is FDA approved for acute gouty arthritis, acute and subacute bursitis, acute nonspecific tenosynovitis, epicondylitis, rheumatoid arthritis, synovitis, or osteoarthritis.

Pediatric dosing - The efficacy and safety of corticosteroids in the pediatric population are based on the well established course of effect of corticosteroids which is similar in pediatric and adult populations. Published studies provide evidence of efficacy and safety in pediatric patients for the treatment of nephrotic syndrome (>2 years of age), and aggressive lymphomas and leukemias (>1 month of age). Other indications for pediatric use of corticosteroids, e.g., severe asthma and wheezing, rheumatoid arthritis, acute inflammatory arthritis are based on adequate and well-controlled trials conducted in adults, on the premises that the course of the disease.

The adverse effects of corticosteroids in pediatric patients are similar to those in adults. Like adults, pediatric patients should be carefully observed for local symptoms after injection. Pediatric patients who are treated with corticosteroids by any route, including systemically administered corticosteroids, may experience a decrease in their growth velocity. This negative impact of corticosteroids on growth has been observed at low systemic doses and in the absence of laboratory evidence of HPA axis suppression (i.e., cosyntropin stimulation and basal cortisol

plasma levels). Since in this study only two single time local administrations at much lower systemic dosage will be carried out this side effect is not likely and not expected.

For the purpose of comparison, the following is the equivalent milligram dosage of the various glucocorticoids:

Cortisone, 25	Triamcinolone, 4
Hydrocortisone, 20	Paramethasone, 2
Prednisolone, 5	Betamethasone, 0.75
Prednisone, 5	Dexamethasone, 0.75
Methylprednisolone, 4	

These dose relationships apply only to oral or intravenous administration of these compounds. When these substances or their derivatives are injected intramuscularly or into joint spaces, their relative properties may be greatly altered locally, however, systemic doses are significantly lower.

A total of 1ml (40 mg) will be injected intra-articularly after synovial fluid aspiration 'to dryness' either once (at study entry or 2 weeks after injury) or twice (at both study entry and 2 weeks after injury).

Rational for including pediatric population

The specific reason for enrolling the age group of children aged 14-17 is that these children have a musculoskeletal physiology like adults.

- Their major growth plates are closed.
- These patients may be treated surgically like adult patients with exactly the same surgical preparation, technique and rehabilitation as adults.
- Children, particularly girls, between the ages of 14 and 18 have the highest statistical risk in any population of tearing their Anterior Cruciate Ligament.²⁵
- Children in this age group are particularly vulnerable to the later development of osteoarthritis. Lohmander et al showed that young female soccer players in this age group developed symptomatic knee Osteoarthritis secondary to the ACL injury within 12 years of the injury.²⁴ One could therefore argue that particularly children between completed puberty and 18 years of age have to be the patients requiring most of our concern regarding development of OA.

By slowing the initial inflammatory process after injury and preventing the significant quadriceps muscle shutdown early, we aim to work towards this goal in this trial. We therefore conclude that given the limited risk of local side effects and the potential large benefit that this study would provide to the scientific community and its potential to significantly improve and alter patient care of young individuals suffering ACL injuries it is not reasonable to withhold pediatric patients aged 14-17 from this important trial.

RESEARCH OBJECTIVES OF THE CURRENT STUDY:

The research objectives of this study are:

1. Test the efficacy of Triamcinolone to alleviate knee pain (KOOS, IKDC) and improve patient-reported outcomes (PRO) following ACL rupture in a randomized, placebo controlled, double blinded, clinical trial. Triamcinolone will be administered intra-articularly within 1 week of ACL injury or at 2 weeks after ACL injury, or at both time points and compared with saline control injections. Patients will be evaluated at 5 post-injury time points (1-2 days, 12-14 days, 2 weeks post-op, 4 weeks post-op, 6 months

- post-op, and 24 months post-op) following ACL reconstruction.
2. Determine if intra-articular Triamcinolone therapy improves levels of a panel of inflammatory (cytokine), meniscus and cartilage metabolism and oxidative stress biomarkers as measured in synovial fluid from patients at relatively short-term time points after ACL injury (1-7 days, 10-17 days after injury and at time of surgery). Biomarkers to be tested include IL-1 α , IL-1 β , Collagen type I (NtxI) and collagen type II (CTXII) breakdown products, cartilage oligomeric protein (COMP) and glycosaminoglycan (GAG) and Xanthine Oxidase. Additionally, the change in IL-1 α and IL-1 β levels in the Triamcinolone treated and placebo individuals will be evaluated specifically for association with pain and function outcomes.

RESEARCH OBJECTIVES OF EXTENDED FOLLOW-UP SUB-STUDY:

1. Determine if joint health as evaluated by MRI at 24 months following ACL injury is influenced by the initial treatment with Kenalog. Two years following ACL injury MRI analysis using standardized T2-mapping will be performed on 10 control subjects and 10 subjects who have received Kenalog injections.

INVESTIGATIONAL PLAN

Description of Overall Study Design and Plan (See Figure 1 for study timeline)

This study is a multicenter, randomized, placebo controlled, double blinded, clinical trial. This trial will enroll 68 subjects between the ages of 14 and 33. This trial will be conducted at two clinical centers, the University of Kentucky and Vanderbilt University, as well as established criteria and support of the Multicenter Orthopaedic Outcome Network (MOON). A sub-study involving extended follow-up of patients, 24 months post-surgery will occur at the University of Kentucky clinical center only. This sub-study will involve 20 subjects of the initial University of Kentucky cohort returning for one additional follow-up MRI.

Description of observations and measurements to be made in this study:

[figure not shown]
Assessment of Pain and Function by KOOS – This trial will use the standardized patient self-report Knee Injury and Osteoarthritis Outcome Score (KOOS) instrument to assess pain and function in response to the intervention for acute ACL injury. The KOOS consists of 5 subscales (pain, other symptoms, function in daily living, function in sport and recreation, and knee-related quality of life). The 5 separate subscales provide a complete picture of subjects' perceptions of their knee injury and consequences to their daily activities, etc.. KOOS includes the WOMAC osteoarthritis index, which allows for potential comparison with other earlier studies. The KOOS has high test-retest reproducibility (ICC > 0.75). The KOOS subscales for function in sport and recreation and knee-related quality of life have been shown to be the most sensitive subscales pre-operatively and change the most post-operatively (44). This trial will supplement the KOOS with function score assessments from the International Knee Documentation Committee (IKDC) form for evaluation of knee ligament injuries [45]. In addition to the KOOS and IKDC, current physical activity level at the 24 month follow-up study will be evaluated using the MARX activity scale.

Specific Pain assessments - Pain coping strategies are important in understanding improvements in pain and psychological disability [46-48]. This trial will use a simple Likert pain scale, the Coping Strategies Questionnaire (CSQ) and 'pain catastrophizing' as pain assessment tools

(Figure 2). Pain catastrophizing has been identified as one of the strongest predictors of pain and has been defined as "an individual's tendency to focus on and exaggerate the threat value of painful stimuli and negatively evaluate one's own ability to deal with pain." Not only do individuals who catastrophize, experience more experimental pain [49-52] but also, catastrophizing has been shown to account for 7% to 31% of the variance in pain ratings in varied populations of patients having persistent pain. It has been associated with heightened anxiety, depression, increased pain behaviors, increased use of health care services and analgesic medication and thus,

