All biomarker analyses in synovial fluid will be performed by co-Investigator [name] (Duke University).

A portion of previously collected samples will be de-identified and shipped on dry ice to Children's National Medical Center at George Washington University where they will undergo the SOMAscan™ assay. The latest version of the SOMAscan assay measures 1,129 protein analytes in only 150 µl of serum. The assay offers exceptional dynamic range, quantifying proteins that span over 8 logs in abundance (from femtomolar to micromolar), with low limits of detection (38 fMol media LOD) and excellent reproducibility (5.1% median %CV) (<http://www.somalologic.com/Technology/SOMAscan-basic-info.aspx>). Once the analyses are complete any remaining samples at National Medical Center will be destroyed. At no time will anyone at Children's National Medical Center have access to subject identifiers or any other subject data.

Randomization: Patients will be randomized into one of four groups, and there will be 17 subjects per group.

- Group 1: will receive injection of Triamcinolone (40 mg) at time point 1 (1-2 days post injury) and saline placebo at timepoint 2 (12-14 post injury).
- Group 2: will receive a saline placebo injection at time point 1 (1-2 days post injury) and 40 mg Triamcinolone at time point 2 (12-14 days post injury.)
- Group 3: will receive two consecutive injections of 40 mg Triamcinolone, the first at time point 1 and the second at time point 2.
- Group 4 (control group): will receive two consecutive injections of saline placebo. The first at time point 1 and the second at time point 2.

Duration of Patient Enrollment: All subjects enrolled in the study will be followed for six months. Those subjects enrolled at the University of Kentucky site will be followed for 24 months, and 20 subjects from the main study will be recruited and enrolled in the extended follow-up MRI sub-study.

Duration of Study: Study duration will be 36 months from the commencement date. This duration may be extended to reach desired enrollment.

Data Safety and Monitoring Board (DSMB) - A DSMB consisting of 5 individuals (will monitor the study semi-annually and review reportable adverse events to the FDA as well as Vanderbilt and University of Kentucky Institutional Review Boards (IRBs). One of these members will maintain the allocation strategy, available upon request from the DSMB.

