Sample Size and Power Analysis - We used the VAS and WOMAC data from Chevalier et al. as the template for power calculations [4] and the change in KOOS pain and ADL from our study. Chevalier reported a 53% response rate by VAS. Response was defined as a 50% improvement in VAS pain score from baseline. We observed comparable differences in our study (20-30% between outcomes in the IL-1Ra and placebo groups); therefore this dataset is reasonable to estimate study power. Based upon the change in VAS pain score in the Chevalier study, and conservatively estimating a placebo response rate of 30%, the effect size was 0.47 for a dichotomous outcome. At this effect size power for a sample size of 17/group is reasonable (65%) for the weakest possible outcome (i.e., one that only generates a "yes" or a "no" for each patient). Moreover, power is excellent for the continuous KOOS outcomes. With 17 patients per group we achieve 90% power for effect sizes of approximately 0.77 and 80% power for effect sizes of approximately 0.65. These latter effect sizes are in standard deviation multiples. So, for example, if the standard deviation of the VAS is approximately 20, and we expect an improvement of approximately 20 units in the intervention group, we can tolerate an improvement of approximately 7 units in the placebo group and still have 90% power (i.e. the effect size is $(20-7)/20 = 0.65$). Moreover, using the effect size standard benchmarks of 0.50 as moderate and 0.80 as large, we will be powered to detect moderate-to-large effects of the intervention, which is consistent with intuition for a study of this size. Power calculations based on our pilot KOOS data confirm this estimate. The change in KOOS (days 0-4) comparing treatment and placebo groups yielded an effect size of 0.62 for pain and 1.08 for ADL. At a

group size of 17 we will have 80% power to detect a difference in KOOS pain and >99% power to detect a difference in KOOS ADL.

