The power calculations include several caveats. The power calculation was performed based upon the use of a IL-1 receptor antagonist. There is no clinical data available in a young patient population with knee ligament injuries regarding their pain improvement after cortisone injection. The IL1RA data is the most comparable. Cortisone is a wider spectrum anti-inflammatory than IL-1RA and thus may have a larger effect on pain control that may be longer lasting. In that case our study may be over-powered. First, for purposes of power calculation, we have not assumed a full repeated measures analysis, but have instead analyzed change from baseline at a single time point. Second, we note that in trials such as this, the power of a non-parametric analysis is never much lower than its parametric analog (the "asymptotic relative efficiency" of the Wilcoxon test is at least 0.95), leading us to conclude that our parametrically based power calculations should apply with equal force to a non-parametric analysis.

Statistical analyses - Results from a sample of this size may not be normally distributed. Therefore, non-parametric statistical measures may be used. Primary outcome measures evaluating for change in KOOS and IKDC will be assessed at multiple points and will be analyzed for change between groups using Friedman two-way ANOVA for repeated measures. Synovial fluid analyses comparing the three groups at three time points will be analyzed using the Wilcoxon Signed Rank Sum Test with Hochberg corrections for multiple time points. Alternatively, if results are normally distributed or can be transformed (e.g., by log transformation) to meet the criteria for normality for parametric analysis, then repeated measures ANOVA will be utilized comparing treatment groups. P-values of less than or equal to 0.05 will be considered statistically significant. For those subjects enrolled in the extended follow-up sub-study the 24 month time point will be examined as an additional time point. Additionally, correlation analyses will be used to examine the relationship between biomarkers collected at Visits 1-3 and KOOS and IKDC values and MRI findings at 24 month follow-up.

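### The plan does not say which triamcinolone-versus-saline contrasts decide efficacy, or at what level; if all three are read at 0.05 unconditionally, the chance of a false finding is about 12% for one score at one visit

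*Combined protocol and SAP*

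**What the plan says.** Under Randomization, "Patients will be randomized into one of four groups, and there will be 17 subjects per group". Groups 1, 2 and 3 receive triamcinolone at the first time point, at the second, or at both. The only comparator is saline at both: "Group 4 (control group): will receive two consecutive injections of saline placebo". Objective 1 sets the three timings against saline: triamcinolone is to be given "within 1 week of ACL injury or at 2 weeks after ACL injury, or at both time points and compared with saline control injections".

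Under Statistical analyses, change in KOOS and IKDC "will be analyzed for change between groups using Friedman two-way ANOVA for repeated measures". If the data are normal or can be transformed to normality, "then repeated measures ANOVA will be utilized comparing treatment groups". The significance rule is general: "P-values of less than or equal to 0.05 will be considered statistically significant". The one multiplicity correction belongs to the synovial fluid analysis: "Wilcoxon Signed Rank Sum Test with Hochberg corrections for multiple time points".

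Sample Size and Power Analysis treats the question as treatment versus placebo, concluding that at a "group size of 17 we will have 80% power to detect a difference in KOOS pain". It states no alpha. The statistical analysis wording is the same in all three copies of the protocol in the file.

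**The concern.** A test across four groups does not say which regimen differs from saline, and that is what objective 1 asks. Someone will therefore look at Group 1 v 4, Group 2 v 4 and Group 3 v 4. The plan gives no rule for doing so beyond the general 0.05 threshold.

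All three regimens are the same drug, so a positive result in any one could be reported as triamcinolone being effective. The trial is also meant to inform a larger randomised trial, so a timing regimen picked out by chance would be carried forward. The gap remains after one score and one visit have been fixed, so it is separate from the number of KOOS and IKDC scores.

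**Working it through.** **Inputs from the documents.** Four arms of 17; Group 4 is the shared control; threshold 0.05; pilot effect sizes 0.62 (KOOS pain) and 1.08 (KOOS ADL). Sidedness is not stated; two-sided is assumed and the one-sided result is given as the range.

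**1. The plan's own power figures.** For a two-sided 17 v 17 t-test at 0.05, the noncentrality is d/√(2/17), with 32 df and critical value 2.04.
- d = 0.62: noncentrality 1.81, power 42% (plan: 80%).
- d = 1.08: noncentrality 3.15, power 86% (plan: more than 99%).

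The stated figures do not reproduce. That is a separate problem, but it means the figures below start from 42% and 86%, not from the plan's values.

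**2. Correlation between contrasts.** Two contrasts share the Group 4 mean. Their covariance is σ²/17 and each variance is 2σ²/17, so the correlation is 0.5. It follows from equal arms and a shared control and is not an assumption.

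**3. Three contrasts read unconditionally, no drug effect.** With c = 1.96,

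P(at least one) = 1 − ∫ φ(u) [Φ((c − √0.5·u)/√0.5) − Φ((−c − √0.5·u)/√0.5)]³ du = 0.125.

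Simulated null trials with four arms of 17 agree: 12.5% (separate t-tests), 12.4% (pooled variance, 64 df), 12.3% (rank-sum). With one-sided 0.05 tests it is 11.8%. For comparison, independent tests would give 1 − 0.95³ = 14.3%.

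Counting only false benefit under two-sided tests, the figure is 6.3%. One contrast gives 0.05/2 = 2.5%, so the ratio is 6.3/2.5 = 2.5.

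**4. Across-group test used alone, or required to be significant first, no drug effect.** Simulated with an ANOVA F-test: 5.0% alone, 4.1% when the three contrasts follow only after a significant F.

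**5. The same precondition when one regimen works.** Group 3 is given an effect of 1.08 and Groups 1 and 2 none. The F-test is significant in about 90% of trials, and Group 1 or 2 is then declared different from saline in about 9% of all trials, about half of these in the direction of benefit.

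**6. Cost of control.** The Dunnett critical value is about 2.41 on 64 df, or about 0.019 per contrast (Bonferroni: 0.05/3 = 0.0167). Single-contrast power becomes 77% at d = 1.08 and 28% at d = 0.62.

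**7. Visit 2 is different.** The second injection is given at Visit 2. Before it, Groups 1 and 3 have each had one triamcinolone injection, and Groups 2 and 4 have each had saline only. A score taken before that injection therefore supports one comparison of 34 v 34, not three regimen contrasts. The visit schedule lists the questionnaires and the injection together without saying which comes first.

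**The case against.** The strongest reply is that the plan does not test each regimen at 0.05. It names one across-group analysis for KOOS and IKDC and writes no pairwise tests, and on that reading the null error rate is 4–5%. This stands, and it makes the 12% conditional. It does not settle the matter, for two reasons. Nothing in the text makes the across-group test a precondition for regimen claims, and step 5 shows that such a precondition stops protecting once one regimen works. In addition, Friedman's test, which the plan names first, ranks within blocks and does not by itself compare independent arms.

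The 12% counts errors in both directions, while the practical worry is a false claim of benefit. That is also right; the relevant figures are 6.3% against 2.5%.

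A reader might infer that one unusually poor saline group would readily make all three regimens look effective. The design does not support that as a main risk: all three falsely show benefit in only about 0.16% of null trials. The likelier error is one or two spurious regimens.

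A reader might also infer that the trial was sized for one 17 v 17 comparison at the full 0.05. The power section states no alpha, and its figures do not match that design.

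Finally, it can be argued that a small multi-arm study producing preliminary data need not control error across regimens. That position is defensible if stated. The plan does not state it, and its unrestricted 0.05 rule suggests that each p-value can carry a claim.

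**Conclusion.** The concern holds in a conditional form. The plan leaves open which regimen-versus-saline contrasts decide efficacy and at what level. If all three are read at two-sided 0.05 without a precondition, the chance of at least one false finding is about 12% for one score at one visit after Visit 2, or 6.3% for false benefit. If the across-group test stands alone or comes first, the null rate is about 4–5%, but in the one-effective-regimen case examined a preliminary test still leaves about 9%.

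It would be wrong to say that the plan tests each regimen at 0.05 and so has an unconditional 12% error rate; the documents do not write those tests. These figures rest on two-sided testing and on normal data with equal variances; the rank-sum check gave nearly the same null result. The change should be made before unblinding.

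**What to change.** Add to Statistical analyses, in substance:

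*For KOOS and IKDC at visits after Visit 2, Groups 1, 2 and 3 are each compared with Group 4. The three contrasts are tested at an overall two-sided 0.05 using Hochberg's procedure [or Dunnett's test, or a fixed order chosen and justified by the sponsor before unblinding]. At Visit 2, if the questionnaires are completed before the second injection, Groups 1 and 3 combined are compared with Groups 2 and 4 combined.*

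Hochberg is the natural default because the plan already uses it for time points. The documents give no basis for preferring one order of regimens, so that choice is the sponsor's. State also whether the across-group test plays any part in the regimen claims, and whether the Visit 2 questionnaires precede the injection.

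Restate power at the level actually used. The wording needs no extra patients, but single-contrast power falls: under Dunnett from about 86% to 77% at d = 1.08, and from about 42% to 28% at d = 0.62. The shortfall for pain exists before any correction. By the normal approximation, 80% power at 0.62 needs 2(1.960 + 0.842)²/0.62² ≈ 41 per arm uncorrected and 2(2.349 + 0.842)²/0.62² ≈ 53 per arm under Dunnett. A fixed order keeps the full 0.05 for the first contrast, but later regimens can then be claimed only if the earlier ones succeed.
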